#### **12.2 Sample Size/Accrual Rate**

This study will plan to enroll 42 subjects to allow for 34 to be evaluable for the primary endpoints.

We plan to accrue roughly 1 subject per month.

### **12.3 Stratification Factors**

As this is a pilot study with a relatively small number of patients, no stratification is planned. However, sub-group analysis of patients with ECOG PS 2 vs PS 0-1 will be performed for the primary endpoint of the study.

### **12.4 Analysis of Endpoints**

All analyses will be performed in SAS Version 9.4 (SAS Institute, Inc., Cary, North Carolina).

#### **12.4.1 Analysis of Primary Endpoints**

The primary endpoint of the 12-month PFS proportion will be calculated and a 95% confidence interval will be estimated via binomial proportions. A one-group chi-square test will be used to compare the 12-month PFS proportion with a historical 12-month PFS proportion of 18%. PFS will also be estimated using the Kaplan-Meier method, and 95% confidence intervals for PFS estimates (including median PFS) will be calculated using Greenwood's formula.

The primary endpoint of safety will be described by the incidence of  $\geq$  Grade 3 toxicities definitely or probably related to the treatments given (i.e. radiation, immunotherapy, and/or chemotherapy), as reported and graded by NCI CTCAE version 5.0.

Full descriptive analysis of safety will also be conducted (e.g. AEs considered causally related to treatment regimen, serious AEs, AEs leading to discontinuation).

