### **3.2 Scientific Rationale for Study Design**

This is a pilot study to examine the feasibility and preliminary safety and efficacy results of combining chemotherapy and IO therapy with non-ablative radiation in ES-SCLC patients. Given the incidence of SCLC encountered at the involved study sites, a single-arm trial was determined to be more feasible in terms of accrual needed to achieve a statistically significant outcome. The goal of the current trial is to show proof of concept for the therapeutic approach of combining chemotherapy and IO therapy with non-ablative radiation and to provide data that would support a larger, randomized-controlled trial.

As chemotherapy plus IO therapy is already the standard of care treatment for ES-SCLC, the addition of radiation to this approach will be the variable being tested. We will use the results of the CASPIAN study as a historical control for comparison. As such, the study interventions in this trial were chosen to mirror those of the experimental arm (platinum + etoposide + durvalumab) of the CASPIAN trial. As in that trial, PCI and TRT will not be given following completion of chemotherapy and immunotherapy. The endpoints being evaluated in this trial have also been reported for the experimental arm of the CASPIAN study.

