### **12. Statistical Considerations**

#### **12.1 Study Design/Endpoints**

One primary aim of this study is to demonstrate that the addition of radiation to chemotherapy and immunotherapy is associated with an improvement in 12-month PFS from 18% historical control to approximately 38% with the addition of radiation. With a sample size of 34 patients receiving chemotherapy/immunotherapy plus radiation, a one-group chi-square test will have 80% power to detect the difference between a null hypothesis 12-month PFS proportion of 18% (i.e., historical control) and an alternative hypothesis 12-month PFS proportion of 38% (i.e., chemotherapy + immunotherapy + radiation), with a 0.05 two-sided significance level. As well, a sample size of 34 patients will allow a two-sided 95% confidence interval for the expected 12-month PFS proportion (38%) to be constructed to be within  $\pm 16.3\%$  of the observed 12-month PFS proportion.

The second primary aim of this study is to evaluate the safety of combining carboplatin + etoposide chemotherapy, durvalumab immunotherapy, and non-ablative radiation to one or more sites of disease. Due to this, we propose a safety run-in for the first 10 subjects. If there is a 30% or greater incidence of grade 3 or higher toxicities with the proposed treatment regimen, specifically from radiation therapy (with focus on pneumonitis, pericarditis, esophagitis, rib fracture, or hemoptysis) or immune-mediated adverse events (other than thyroid dysfunction), then the radiation regimen will be switched to 5 Gy radiation per day for 5 days. If there is still a 30% or greater incidence of grade 3 or higher toxicities from radiation therapy or immune-mediated adverse events among the subsequent 10 subjects, then the study will be terminated. If this does not occur, then accrual will continue until 34 total subjects are evaluable.

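### Does leaving the method for the 95% interval on 12-month PFS unnamed call for a change to the plan?

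*Combined protocol and SAP*

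**What the plan says.** Section 12.4.1 defines the efficacy analysis in three steps. The 12-month PFS proportion is calculated and "a 95% confidence interval will be estimated via binomial proportions". Next, "A one-group chi-square test will be used to compare the 12-month PFS proportion with a historical 12-month PFS proportion of 18" percent. Last, PFS is additionally estimated by Kaplan-Meier, and "95% confidence intervals for PFS estimates (including median PFS) will be calculated using" Greenwood's formula.

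The section does not name the type of binomial interval, does not mention a continuity correction, and gives no transformation for the Greenwood interval. Section 12.4.2 describes the intervals for objective response and 12-month OS in the same general terms, but plans no test for either.

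Section 12.1 gives the planning basis: "With a sample size of 34 patients receiving chemotherapy/immunotherapy plus radiation, a one-group chi-square test will have 80% power" for 18% against 38% at a two-sided 0.05 level. It adds that 34 patients allow "a two-sided 95% confidence interval for the expected 12-month PFS proportion (38%) to be constructed" to within ±16.3%. Section 10.1 defines the primary endpoint as the proportion without progression at 12 months. Section 3.2 sets the context: "This is a pilot study to examine the feasibility and preliminary safety and efficacy results".

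**The concern.** The only clue to the intended interval is the ±16.3%, which is a Wald figure. The Wald interval is known to fall short of its nominal coverage in small samples, and 34 is small. If it were used, the main efficacy estimate would carry an interval labelled 95% that covers less often than that.

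There is also a risk of an inconsistent report. A one-group chi-square test takes its standard error from the null rate of 18%. The Wald interval takes its standard error from the observed rate. The two can therefore disagree about 18%, and they do so at the smallest count that the uncorrected test declares positive. A significant p-value could then stand beside one or two intervals that include the historical rate. Because the method is unnamed, an analyst could in principle choose among intervals after seeing the result.

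**Working it through.** Inputs, all from Section 12.1: n = 34 evaluable, null rate 0.18, alternative 0.38, two-sided alpha 0.05, stated power 80%, stated half-width 16.3%.

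**1. The planning precision.** Wald half-width: 1.96 × √(0.38 × 0.62 / 34) = 1.96 × 0.0832 = 0.163. This reproduces ±16.3%.

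**2. The planning power.** Uncorrected test, normal approximation: Φ[(0.20 × √34 − 1.96 × √(0.18 × 0.82)) / √(0.38 × 0.62)] = Φ[(1.166 − 0.753) / 0.485] = Φ(0.851) = 0.803. Exact binomial power:
- uncorrected, reject at 11/34 or more: 80.2%
- continuity-corrected, reject at 12/34 or more: 68.8%

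Only the uncorrected test matches the stated 80%. Its exact two-sided size is 4.2%.

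**3. The test around the boundary.** The null standard error is √(0.18 × 0.82 / 34) = 0.0659.
- 10/34: p = 0.083, not rejected
- 11/34: z = (0.3235 − 0.18) / 0.0659 = 2.18, p = 0.029, rejected
- 11/34 with a correction of 1/68: z = (0.1435 − 0.0147) / 0.0659 = 1.955, p = 0.0506, not rejected

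**4. Intervals at 11/34.**

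| Method | 95% limits | Contains 18%? |
|---|---|---|
| Wald: 0.3235 ± 1.96 × √(0.3235 × 0.6765 / 34) | 16.6% to 48.1% | yes |
| Clopper-Pearson | 17.4% to 50.5% | yes |
| Wilson score | 19.1% to 49.2% | no |
| Greenwood, plain | 16.6% to 48.1% | yes |
| Greenwood, log-log | 17.6% to 48.0% | yes |
| Greenwood, log | 19.9% to 52.6% | no |

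The Greenwood rows assume that nobody is censored before 12 months; the plain form then equals Wald.

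**5. How far the disagreement reaches.** Over all counts from 0 to 34, compared with the uncorrected test:
- Wald disagrees at 2 and 11
- Clopper-Pearson disagrees at 11 only
- Wilson never disagrees, because it inverts the same test

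At 2/34 the observed rate is below 18%, so that disagreement has no bearing on a claim of benefit. At 12/34 the lower limits are 19.2% (Wald), 19.7% (Clopper-Pearson) and 21.5% (Wilson), and all three exclude 18% from there upward. The probability of exactly 11/34 is 11.5% at a true 38% and 1.9% at a true 18%.

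**6. Exact coverage at n = 34.** For each true rate, this is the sum of the binomial probabilities of the counts whose interval contains that rate.

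| Method | True 18% | True 38% | Mean, 18–45% | Minimum, 18–45% |
|---|---|---|---|---|
| Wald | 94.6% | 91.8% | 93.1% | 88.0% |
| Wilson | 95.9% | 95.0% | 95.1% | 92.4% |
| Clopper-Pearson | not tabulated | 96.5% | 96.8% | 95.1% |

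The range 18–45% is an illustrative choice and does not come from the documents. The Wald mean depends on it: 92.9% over 18–38%, and 92.7% over 10–90%.

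**The case for a change.** The best argument for a change is that this is a co-primary endpoint with a formal test, meant to support a larger randomised trial, and that a few sentences would remove all doubt. At 11/34 the unstated continuity correction moves the p-value from 0.029 to 0.0506, so an unstated detail decides the result there. Whether the interval printed beside that p-value includes 18% then depends on a method nobody has named. The disagreement is also not peculiar to 34 patients: Wald and the uncorrected test differ for at least one count at every evaluable number from 30 to 42.

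Part of this stands. The method is unnamed, and an awkward pairing at 11/34 is possible. The rest is weaker.

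- The correction is settled in substance. Section 12.4.1 mentions none, and the power in Section 12.1 cannot be obtained with one.
- The order of the procedures can be read from the text. The chi-square test is the one that is powered and the one used for the comparison with 18%. The binomial interval describes the estimate, Kaplan-Meier is introduced as an addition, and no interval is a decision criterion.
- The shortfall in coverage arises only if Wald is chosen. A half-width used to describe planning precision does not bind the analysis.
- No single replacement is clearly right. Wilson agrees with the test at every count, but its own coverage is below 95% at about 54% of the true rates from 18% to 45%. Clopper-Pearson never falls below 95%, yet it keeps the conflict at 11/34. There the exact upper tail under 18% is 3.16%, so the result is borderline on an exact basis whichever interval is printed.

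**Conclusion.** No change to the plan is needed. This is a missing detail that an analyst fills sensibly, together with a trade-off between agreement with the test and guaranteed coverage on which statisticians can reasonably differ. Followed as written, the plan gives a valid test with exact size 4.2% and exact power 80.2%, and its planning figures reproduce.

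The largest practical effect is one count, 11/34, with probability 11.5% if the true rate is 38%. There a significant test may sit beside an interval that contains 18%. If Wald were used, coverage would be 94.6% and 91.8% at the two rates the plan names. That is a modest shortfall in a pilot whose results are described as preliminary. In Section 12.4.2 no test is planned, so no such conflict can arise.

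The conclusion rests on three assumptions: 34 evaluable patients, 12-month status known for all of them, and the uncorrected form of the test, which is inferred from the stated power.

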## **8.3 Lost to Follow Up**

A participant will be considered lost to follow-up if he or she fails to return for scheduled visits for 3 months and is unable to be contacted by the study site staff.

The following actions must be taken if a participant fails to return to the clinic for a required study visit:

- The site will attempt to contact the participant and reschedule the missed visit within 14 days and counsel the participant on the importance of maintaining the assigned visit schedule and ascertain if the participant wishes to and/or should continue in the study.
- Before a participant is deemed lost to follow-up, the investigator or designee will make every effort to regain contact with the participant (where possible, 3 telephone calls and, if necessary, a certified letter to the participant's last known mailing address or local equivalent methods). These contact attempts should be documented in the participant's medical record or study file.
- Should the participant continue to be unreachable, he or she will be considered to have withdrawn from the study with a primary reason of lost to follow-up.

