## **10. Measurement of Effect**

### **10.1 Progression-Free Survival**

PFS will be defined as the time from first study treatment to the point of either radiographic progression of malignancy by RECIST 1.1 criteria or death. Death will be considered clinical progression if the cause of death is felt to be due to the underlying malignancy (vs due to toxicity or a non-malignancy related cause such as accident). Median PFS will be estimated using the Kaplan-Meier method.

The proportion of subjects without progression (as defined above) at 12-months after start of study treatment will constitute the 12-month PFS rate, which is the primary endpoint of this study.

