## **10.2 Overall Survival**

OS will be defined as the time from first study treatment to the time of death from any cause. Median OS will be estimated using the Kaplan-Meier method. The proportion of subjects still alive at 12-months after start of study treatment will constitute the 12-month OS rate.

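### The primary 12-month PFS test is a raw binomial proportion with no rule for treated subjects who leave progression-free before month 12, and the Kaplan-Meier estimate that could handle them is not tied to the test

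*Combined protocol and SAP*

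**What the plan says.** Section 10.1 defines the endpoint: "The proportion of subjects without progression (as defined above) at 12-months after start of study treatment will constitute the 12-month PFS rate". Section 12.4.1 estimates it as a binomial proportion with a binomial 95% confidence interval and then tests it: "A one-group chi-square test will be used to compare the 12-month PFS proportion with a historical 12-month PFS proportion of 18"%. The same paragraph adds a Kaplan-Meier estimate with Greenwood intervals, but neither the test nor the comparison with 18% uses it. Twelve-month OS is built the same way (Sections 10.2 and 12.4.2): "The proportion of subjects still alive at 12-months after start of study treatment will constitute the 12-month OS rate".

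Subjects can leave early. Section 8.1 (item 5) and Section 8.2 allow withdrawal of consent. Under Section 8.3 a subject who cannot be reached is closed out: "he or she will be considered to have withdrawn from the study with a primary reason of lost to follow-up". Section 8.2 does not replace treated subjects who leave.

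Section 12.2 sets the numbers: "This study will plan to enroll 42 subjects to allow for 34 to be evaluable for the primary endpoints". Evaluability is defined for toxicity (12.6.1) and for response (12.6.2), but not for PFS. No section gives a censoring rule, a missing-status rule or a PFS denominator.

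**The concern.** A subject who leaves progression-free at month 4 has no 12-month status. The analyst must drop that subject, call the subject a success or call the subject a failure, and the plan does not choose. The three choices give different estimates, error rates and power. In an open-label, single-arm trial the choice could be made after the outcomes are known.

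At stake is the one formal efficacy comparison, with the historical 18%. If anyone is censored before month 12, the binomial and Kaplan-Meier 12-month figures can also differ, and nothing says which one governs.

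**Working it through.** **Inputs from Section 12.1.** Null: "a null hypothesis 12-month PFS proportion of 18% (i.e., historical control". Alternative: "an alternative hypothesis 12-month PFS proportion of 38% (i.e., chemotherapy + immunotherapy + radiation". Test level: "with a 0.05 two-sided significance level". Stated result: n = 34, power 80%, 95% interval ±16.3%.

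**Step 1: reproduce the plan's figures.**
- n = [1.960·√(0.18·0.82) + 0.842·√(0.38·0.62)]² / 0.20² = (0.753 + 0.409)² / 0.04 = 33.7 (computed before rounding), so 34.
- With n = 34 the chi-square rejects upward at 11 or more: z = (11 − 6.12)/√(34·0.1476) = 2.18, while 10 gives 1.73.
- Exact binomial power at 38% is 80.2% and upper-tail error at 18% is 3.2%.
- Half-width: 1.96·√(0.38·0.62/34) = 16.3%.

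The sizing is correct when all 34 statuses are known.

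**Step 2: model the loss (assumed).** PFS is exponential with rate λ = −ln(p)/12, which is 0.0806 per month at p = 38% and 0.1429 at p = 18%. Loss is independent and exponential with rate η. The share lost progression-free before month 12 is d = η/(λ+η)·(1 − e^(−12(λ+η))). I solved for η at d = 5%, 10% and 19%; 8/42 = 19.0%. The share observed progression-free at month 12 is s = e^(−12(λ+η)):
- true 38%: 0.351, 0.321, 0.270
- true 18%: 0.161, 0.143, 0.113

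**Step 3: score the lost subjects three ways.** The expected proportion is s/(1−d) if dropped, s + d if counted as successes and s if counted as failures (computed before rounding). Rejection rates are exact binomial.

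| Handling | No loss | 5% | 10% | 19% |
|---|---|---|---|---|
| Dropped: expected rate, true 38% | 38% | 36.9% | 35.7% | 33.4% |
| Dropped, 34 analysed: power | 80.2% | 76% | 72% | 61% |
| Dropped from 42 treated: power | 86.5% | 82% | 77% | 61% |
| Success: expected rate, true 18% | 18% | 21.1% | 24.3% | 30.3% |
| Success, n=34: upper-tail error | 3.2% | 8.7% | 18.5% | 46% |
| Failure, n=34: upper-tail error | 3.2% | 1.5% | 0.6% | 0.1% |
| Failure, n=34: power | 80.2% | 69% | 55% | 30% |

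**Step 4: direction of the bias from dropping.** Let q be the 12-month PFS the lost subjects would have had. The retained rate is (p − d·q)/(1 − d), which is below p only if q > p. Independent loss guarantees this, because the subject has already survived part of the year progression-free. At 10% loss q is about 0.585, and (0.38 − 0.0585)/0.90 = 0.357. If those who leave are doing worse, say q = 0.20, the result is (0.38 − 0.02)/0.90 = 0.40, which is biased upward.

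**Step 5: which Kaplan-Meier test.** By simulation, a Wald test on the log-log Greenwood scale has power of only about 69% at n = 34 and 78% at n = 42 with no loss at all. An alternative uses the null variance. Let V be the Greenwood variance of the 12-month estimate Ŝ, let n_eff = Ŝ(1−Ŝ)/V, and let z = (Ŝ − 0.18)/√(0.18·0.82/n_eff). Without censoring V = Ŝ(1−Ŝ)/n, so n_eff = n and z² is the planned chi-square. Simulated under the Step 2 model with censoring at the time of loss:
- upper-tail error is about 3% to 3.7%
- power with no loss is about 80% at n = 34 and 86.5% at n = 42
- power with 42 treated is about 86%, 84% and 79% at 5%, 10% and 19% loss (reruns differ by about one point)

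**The case against.** The strongest reply is that little loss is likely and the plan has a margin. Stopping treatment is not leaving the study (8.1), imaging continues every 8 weeks until progression (6.1.2.5), follow-up runs 2 years or until death (7.8), and loss requires three months' absence and repeated contact attempts (8.3). A Kaplan-Meier curve will exist anyway, and Section 3.2 calls this a pilot meant to support a randomized trial. All of this stands. It lowers the likely loss but supplies no scoring rule.

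Four stronger readings are tempting, and the documents do not support them.
- **Loss necessarily takes power below 80%.** With 42 treated and 5% dropped, power is 82%. Comparing dropping with 34 analysed against Kaplan-Meier with 42 treated would exaggerate the gain.
- **Dropping always biases the rate downward.** Step 4 shows that the direction depends on who leaves.
- **The plan expects 19% early loss.** The eight extra subjects cover undefined non-evaluability, which could include subjects never treated or not completing radiation.
- **The plan instructs that lost subjects be successes.** Section 10.1 can be read that way, but it refers to status at 12 months, which these subjects lack.

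**Conclusion.** The point holds as a gap in the primary analysis. The test has no valid score for a treated subject who leaves progression-free before month 12, and the estimator that accommodates such subjects is left outside the test. The gap is material even at low loss: at 5%, the success scoring takes the upper-tail error from 3.2% to 8.7%, and the failure scoring takes power from 80.2% to 69% (both n = 34).

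These sizes rest on exponential PFS, loss independent of prognosis and assumed loss rates. The 19% column is an upper scenario. The 34-subject calculation is sound, and the trial remains interpretable. This should be corrected before outcomes are analysed.

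**What to change.** - **12.4.1, estimate.** Make the 12-month Kaplan-Meier estimate in all treated subjects the primary PFS estimate. Censor subjects who withdraw or are lost progression-free at their last tumour assessment. Report a Greenwood confidence interval.
- **12.4.1, test.** Compare the estimate with 18% using the null-variance statistic of Step 5. Do not make the log-log Wald test primary, because it loses power even with complete data.
- **12.4.1, sensitivity.** Keep the binomial chi-square with unknown 12-month status scored as failure, as a conservative check.
- **12.4.2.** Report 12-month OS from the Kaplan-Meier curve in the same way.
- **12.1.** State that 80% power at n = 34 applies to complete 12-month status under this test. Give the power at the assumed loss: with 42 treated, about 86%, 84% and 79% at 5%, 10% and 19%.

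The cost is statistical wording only, with no change to visits, treatment or enrolment. The downside is small: the interval and test are asymptotic and still assume non-informative censoring, which is why the failure-scored analysis should stay beside them.

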## 1.1 Schema

## 1.2 Study Objectives

### **1.2.1 Primary Objective**

To examine the safety and efficacy of adding multi-site, non-ablative radiation to standard systemic therapy with carboplatin or cisplatin and etoposide plus durvalumab for patients with extensive-stage small cell lung cancer.

Co-Primary Endpoints:

- 12-month Progression-Free Survival
- Safety in terms of Incidence of  $\geq$  Grade 3 Toxicities related to therapy given

Secondary Endpoints:

- 12-month Overall Survival
- Response Rate
- Median Progression-Free Survival
- Median Overall Survival
- Pattern of Disease Progression

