#### **13.2.3 Investigational Agent or Device Risks (Expected Adverse Events)**

As the combination of platinum + etoposide chemotherapy and Durvalumab immunotherapy is now FDA-approved for patients with ES-SCLC, the "investigational

agent" in this study will be the sub-ablative radiation. Mild to moderate (grade <3) adverse events from thoracic radiation include the following: esophagitis, dermatitis, radiation recall reaction, pleural effusion, pericardial effusion, pleuritic pain, non-cardiac chest pain, chest wall pain, pneumonitis, atelectasis, cough, dyspnea, pulmonary fibrosis, generalized muscle weakness, fatigue, photosensitivity, telangiectasias, FEV decrease, WBC decrease, lymphocyte count decrease, and neutrophil count decrease. Severe adverse events (grade ≥3) from radiation may also include the above mentioned plus those listed in Table 6.

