#### **13.2.4 Adverse Event Characteristics and Related Attributions**

**CTCAE term (AE description) and grade:** The descriptions and grading scales found in the revised NCI Common Terminology Criteria for Adverse Events (CTCAE) version 5.0 will be utilized for AE reporting. A copy of the CTCAE version 5.0 can be downloaded from the CTEP web site (<http://ctep.cancer.gov>).

- **Attribution** of the AE:

- Definite – The AE is *clearly related* to the study treatment.
- Probable – The AE is *likely related* to the study treatment.
- Possible – The AE *may be related* to the study treatment.
- Unlikely – The AE is *doubtfully related* to the study treatment.
- Unrelated – The AE is *clearly NOT related* to the study treatment.

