**Table 4: Adverse events of any cause (safety population)**

Table S5: Treatment-related adverse events as assessed per the investigator (safety population)

	Durvalumab + EP (n=265)		EP (n=266)	
	Any grade	Grade 3 or 4	Any grade	Grade 3 or 4
Any treatment-related event, n (%)	237 (89%)	121 (46%)	240 (90%)	138 (52%)
Any treatment-related serious event, n (%)	35 (13%)	25 (9%)	50 (19%)	45 (17%)
Any treatment-related event leading to discontinuation, n (%)*	15 (6%)	3 (1%)	13 (5%)	4 (2%)
Any treatment-related event leading to death, n (%)†	5 (2%)	—	2 (1%)	—
Treatment-related adverse events with an incidence of $\geq 5\%$ in any grade category or events of grade 3 or 4 with an incidence of $\geq 2\%$ in either arm, n (%)‡				
Neutropenia	104 (39%)	61 (23%)	116 (44%)	86 (32%)
Anaemia	85 (32%)	21 (8%)	103 (39%)	38 (14%)
Alopecia	74 (28%)	3 (1%)	85 (32%)	2 (1%)
Nausea	74 (28%)	0	75 (28%)	5 (2%)
Thrombocytopenia	37 (14%)	14 (5%)	48 (18%)	24 (9%)
Vomiting	32 (12%)	0	38 (14%)	2 (1%)
Decreased appetite	33 (12%)	1 (<1%)	35 (13%)	1 (<1%)
Leucopenia	36 (14%)	15 (6%)	32 (12%)	14 (5%)
Fatigue	30 (11%)	2 (1%)	36 (14%)	3 (1%)
Asthenia	27 (10%)	2 (1%)	31 (12%)	2 (1%)
	Durvalumab + EP (n=265)		EP (n=266)	
	Any grade	Grade 3 or 4	Any grade	Grade 3 or 4
Neutrophil count decreased	24 (9%)	16 (6%)	28 (11%)	17 (6%)
Constipation	23 (9%)	0	24 (9%)	0
Diarrhoea	17 (6%)	2 (1%)	15 (6%)	2 (1%)
Febrile neutropenia	15 (6%)	13 (5%)	17 (6%)	17 (6%)
White blood cell count decreased	12 (5%)	4 (2%)	17 (6%)	6 (2%)
Platelet count decreased	14 (5%)	4 (2%)	13 (5%)	6 (2%)
Paraesthesia	14 (5%)	0	11 (4%)	0
Hypothyroidism	23 (9%)	0	0	0
Hyperthyroidism	22 (8%)	0	0	0
Lipase increased	10 (4%)	8 (3%)	2 (1%)	1 (<1%)

Data cutoff date: March 11, 2019. Listed are all adverse events assessed by the investigator as possibly related to any study treatment that occurred during the treatment period and up to 90 days after the last dose of durvalumab or EP or up to the start of any subsequent therapy (whichever occurred first). \*Includes patients who permanently discontinued at least one study drug. †Treatment-related adverse events leading to death in the durvalumab plus EP arm were cardiac arrest, dehydration, hepatotoxicity, pancytopenia, and sepsis in one patient each. Treatment-related adverse events leading to death in the EP arm were pancytopenia and thrombocytopenia/haemorrhage in one patient each. ‡The events are listed in descending order of frequency across both treatment arms. EP=platinum-etoposide.

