Other rare/miscellaneous §	2 (1%)	0	0	0

Data cutoff date: 11 March 2019. Listed are all immune-mediated adverse events that occurred during the treatment period and up to 90 days after the last dose of durvalumab or EP or up to the start of any subsequent therapy (whichever occurred first). \*Grade 5 immune-mediated adverse events occurred in one patient receiving durvalumab plus EP (hepatotoxicity) and one patient receiving EP (pneumonitis). †An immune-mediated adverse event is defined as an event that is associated with drug exposure and 21 consistent with an immune-mediated mechanism of action, where there is no clear alternate etiology and the event required treatment with systemic corticosteroids or other immunosuppressants and/or, for specific endocrine events, endocrine therapy. §The events in the 'other rare/miscellaneous' category were both arthritis.

EP=platinum-eposide.

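### The co-primary safety count omits events rated possibly related, so it has no like-for-like figure in the historical control

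*Combined protocol and SAP*

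**What the plan says.** - **Endpoint list (Section 1.2.1).** The safety endpoint is the incidence of at least "Grade 3 Toxicities related to therapy given", with no attribution cut-off.
- **Analysis (Section 12.4.1).** The count is narrowed to "toxicities definitely or probably related to the treatments given (i.e. radiation, immunotherapy, and/or chemotherapy". It will be described; no test, margin or threshold is set. A fuller descriptive analysis is also promised, including causally related events, but without saying which attribution levels that covers.
- **Attribution scale (Section 13.2.4).** There are five levels. Between Probable and Unlikely stands "Possible – The AE *may be related* to the study treatment".
- **Control (Section 3.2).** CASPIAN is the historical control, and "The endpoints being evaluated in this trial have also been reported for the experimental arm of the CASPIAN study". The statement is not limited to efficacy.
- **Control's treatment-related table (Appendix A, Table S5, footnote).** "Listed are all adverse events assessed by the investigator as possibly related to any study treatment".

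No section reconciles the rule in 12.4.1 with the rule in Table S5.

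**The concern.** With one arm, added harm from radiation can be seen only against an outside rate. Section 2.5.1 frames the safety aim that way: it looks for an increase in immune-mediated and in radiation-related events over the control regimen. The natural benchmark for a treatment-related grade 3 or higher rate is Table S5, but its footnote describes a wider attribution rule than the one in 12.4.1. The other control figures that 2.5.1 quotes (62% any-cause grade 3 or 4, 5% immune-mediated grade 3 or 4) are not on the definite-or-probable scale either.

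A reader who sets the trial's rate beside 46% would compare a narrow count with a wide one. Safety is co-primary and Section 3.2 says the data should support a randomized trial, so a real excess could be read as no increase.

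**Working it through.** **Inputs from the documents**
- Control, treatment-related, grade 3 or 4 (Table S5): 121 of 265.
- Control, treatment-related deaths (Table S5): 5.
- Control, any cause, grade 3 or 4 (Table 4): 163 of 265.
- Trial size (Section 12.2): 42 enrolled, 34 evaluable. Section 12.6.1 makes every treated subject evaluable for toxicity.

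**Assumed input**
- *s*, the share of patients with a related grade 3 or higher event whose only such events are rated Possible. The documents do not give it; a range is shown.

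**Step 1: reproduce the control figures.** 121/265 = 45.7%, printed as 46%. 163/265 = 61.5%, printed as 62%. The trial also counts grade 5. If none of the 5 treatment-related deaths is among the 121, the control's grade 3 to 5 rate is at most (121 + 5)/265 = 47.5%.

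**Step 2: direction.** Let *q* be the trial's rate counting definite, probable and possible events. The rate under 12.4.1 is *r* = *q*(1 − *s*). Since *s* is between 0 and 1, *r* cannot exceed *q*.

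**Step 3: size, over a range of *s*.** The middle column takes a trial whose inclusive rate equals the control's 45.7%. The right column gives the inclusive rate that would be reported as 45.7%, that is *q* = 0.457/(1 − *s*).

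| *s* | Reported rate if *q* = 45.7% | Inclusive rate that reads as 45.7% |
|---|---|---|
| 10% | 41.1% | 50.7% |
| 20% | 36.5% | 57.1% |
| 30% | 32.0% | 65.2% |

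The excess that goes unseen is about 5, 11 or 20 points. Starting from 47.5%, the middle column becomes 42.8%, 38.0% and 33.3%.

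**Step 4: set against sampling error.** The 95% half-width around 45.7% is 1.96 × √(0.457 × 0.543/34) = 16.7 points with 34 patients, and 1.96 × √(0.457 × 0.543/42) = 15.1 points with 42. The shortfalls in the middle column (4.6, 9.1 and 13.7 points) lie inside that. They are systematic, however, and the interval does not allow for them.

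**The case against.** The strongest reply is that no safety comparison with the control is planned. Safety is described, the only test against a historical figure is 12-month PFS against 18%, and the safety decisions use an absolute threshold of 30% in 10 subjects. A definite-or-probable cut-off is also a legitimate choice where chemotherapy and tumor are rival causes. This stands: no test, power or stopping decision depends on the point. It does not remove the problem of interpretation, because 3.2 invites the comparison and 2.5.1 frames the aim as an increase.

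A second reply is that the data and a full descriptive analysis are already planned. The data are, but the wording in 12.4.1 does not commit to a possible-inclusive or an all-cause grade 3 or higher count.

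Three stronger readings are tempting, and the documents do not support them.

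- *The trial's rate will come out below the control's.* It is low only relative to an inclusive count in the same patients. The raw figure could still exceed 46% if radiation adds toxicity. The event windows also differ: Table S5 stops 90 days after the last dose or at subsequent therapy, whichever comes first. This trial continues evaluation after progression (6.1.3) and records events until 7 days (non-serious) or 90 days (serious) after the last day of participation (13.6). That may raise its count.
- *The control's own tables show how large the shortfall is.* The fall from 163 to 121 is the step from any cause to possibly related, not from possible to probable. Section 13.2.3 lists among radiation effects "chest wall pain, pneumonitis, atelectasis, cough, dyspnea, pulmonary fibrosis", and cough and dyspnoea appear in Table 4 but not in Table S5. That listing rests largely on any-grade frequency, though; at grade 3 or 4, Table 4 has only 2/265 and 5/265.
- *The run-in rule also drops possible events.* Section 12.1 counts grade 3 or higher toxicities "specifically from radiation therapy (with focus on pneumonitis, pericarditis, esophagitis, rib fracture, or hemoptysis) or immune-mediated adverse events (other than thyroid dysfunction". It names no attribution category and does not refer to 12.4.1.

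**Conclusion.** The point holds as a matter of comparability. The co-primary safety rate is on a narrower attribution scale than the control's treatment-related table. No control figure in the documents matches it, and relative to an inclusive count it can only be equal or lower. The size is unknown: the figures of about 51%, 57% and 65% reading as 46% depend on assumed possible-only shares of 10%, 20% and 30%. Cytopenias make up much of the control's total and may be attributed with more confidence, so the true share could be at the low end.

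One further assumption is that the control's possibly related corresponds to this trial's Possible level. The documents do not reproduce the control's scale, which may have been a yes-or-no question. Differences in event window and in grade 5 counting would remain after any change. This is a cheap and worthwhile improvement to how a descriptive endpoint is reported, not an error that affects the trial's decisions.

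**What to change.** In Section 12.4.1:

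1. Report grade 3 or higher events rated possibly, probably or definitely related as the count set beside Table S5. This can be the primary count, or a prespecified count next to the definite-or-probable one if the sponsor prefers to keep that as primary.
2. Report all-cause grade 3 or higher events beside Table 4.
3. List pneumonitis, esophagitis, pericarditis, hemoptysis and rib fracture separately, whatever their attribution.
4. Note with the comparison that event windows and grade 5 handling still differ.

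No change to the run-in rule is needed for this point.

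The cost is wording and a little extra analysis. Section 13.2.4 already provides the five attribution levels, and Section 13.6 requires every adverse event on study to be documented whatever its relationship to treatment. The downside is that the inclusive rate will be higher than under the current definition and will include some events caused by the disease.
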